The FDA Mifeprex (mifepristone) information describes teratology studies in mice, rats and rabbits at doses of 0.25 to 4.0 mg/kg (less than 1/100 to approximately 1/3 the human exposure based on body surface area), stating that because of the antiprogesterone activity of mifepristone, fetal losses were much higher than in control animals. Skull deformities were detected in rabbit studies at approximately 1/6 the human exposure, although no teratogenic effects of mifepristone have been observed to date in rats or mice. These deformities were most likely due to the mechanical effects of uterine contractions resulting from inhibition of progesterone action. As stated above, mifepristone will be administered to term pregnant participants and will be far outside of the window of organogenesis (fetal development), thus risk for teratogenicity is nullified by the fact that the study will take place in term pregnancies long after fetal development is completed.

Safety measures for this study include the following:

- Obtain VITALS (blood pressure, mean arterial blood pressure, heart rate, respiratory rate) throughout labor induction, every 15 minutes for the first hour of the induction process and then hourly during the first 4 hours of the induction process. (see table below for reference range in pregnancy). In addition, oral temperature will be taken per standard protocol
- Pregnant patients in this study may receive up to a maximum dose of 200 mg mifepristone only; this is the max dose per course as outlined by the package label instructions. Each dose will be given as 200 mg orally, once at the induction initiation
- Monitor patients for adverse symptoms of mifepristone
- All patients will undergo continuous electronic fetal heart rate monitoring and tocometry until the time of delivery

Cardiac, Respiratory and Hematologic Physiologic Changes in Pregnancy

	Direction of Change	Percentage of Change or Normal Range in Pregnancy
Blood volume	^	30%-40% increase
Heart rate	^	Increases by 10-20 bpm
Cardiac output	^	30%-60% increase
Systemic vascular resistance	4	25%-30% decrease
Blood pressure	4	10-15 mm Hg decrease in first two trimesters
Colloid oncotic pressure	4	10%-15% decrease
Total lung capacity	ψ	4%-5% decrease
Functional residual capacity	÷	20% decrease
Diffusion capacity	↔	No change
Tidal volume	^	Increased
Respiratory rate	↔	No change
Minute ventilation	^	50% increase
PaO ₂	1	Average 100-105
PcaCo ₂	÷	Average 28-32
рН	†	Mild respiratory alkalosis

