A-a gradient	^	Increase in late gestation to approximately 20
Protein S	÷	
Activated protein C resistance, fibrinogen, factor V, VIII, IX, X	^	
Plasminogen activator inhibitor type 1 and 2		
Activity of tissue plasminogen	J.	

Modified from Miller MA, Bourjeily G. Management of the critically ill pregnant patient. Pulmonary and Critical Care Update (PCCU). April 2009, 23 (Lesson 8); with permission.

Source: Williams Obstetrics and Gynecology, 25th Edition

[figure not shown]
Vital signs which suggest hemodynamic instability or suspicion for sepsis

- Oral Temperature $<36 \text{ }^{\circ}\text{C}$ (96.8 $^{\circ}\text{F}$) or $>38 \text{ }^{\circ}\text{C}$ (100.4 $^{\circ}\text{F}$)
- Heart rate > 110 beats per minute or <50 beats per minute
- MAP <65 mm Hg
- Respiratory rate > 24 breaths per minute or less than < 10 breaths per minute

If the patient experiences 2 vital signs that are outside of normal parameters, the standard of care work up will be initiated.

If the patient experiences a fever in labor, per standard of care, antibiotics are started, and an infectious workup is initiated. If the patient has a fever with abnormal vital signs per CMQCC guidelines (see below), assessment for infection is initiated per standard of care.

CMQCC Maternal Sepsis Evaluation Flow Chart

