6.2 Induction of Labor: Study Groups

At LPCH cervical preparation typically begins with prostaglandins (misoprostol and dinoprostone), 12-hours of transcervical (Cook) balloon placement, or misoprostol and Cook balloon used concurrently. For the purposes of our study, all patients will receive the standard of care for labor induction at LPCH, starting with mechanical induction of labor with the transcervical (Cook) balloon. The Cook balloon will remain in place for a maximum of 12 hours. After 12 hours of Cook balloon placement, the OB provider will deflate the Cook balloon and perform a cervical exam. If the balloon spontaneously expels prior to 12 hours, the time will be noted and a cervical exam performed. The balloon will be removed at any point in the setting of spontaneous rupture of membranes (SROM) per standard of care, to minimize risk of intraamniotic infection. After a balloon expulsion, balloon removal in the setting of SROM or after 12 hours of balloon placement and removal, the provider will manage the labor induction based on standard of care practice, including using up-titration of oxytocin, amniotomy when deemed safe and appropriate, and transitioning to cesarean or operative birth if deemed necessary by the provider. Patients who receive misoprostol will be eligible to receive additional doses of misoprostol 50 - 100 mcg, because of its known safety. Patients who receive mifepristone will not be eligible for additional doses of misoprostol because based on the pharmacokinetics of mifepristone, the ripened cervix could potentiate uterine tachysystole.

Once the patient achieves complete cervical dilation, time spent in the second stage of labor will be at the discretion of the OB provider given variability among patients and providers.

As the standard of care, oxytocin is indicated when a modified Bishop score of 8 or greater is observed or if spontaneous rupture of membranes occurs during the ripening process. Intravenous oxytocin will begin at 1 milliunits per minute about 12 hours after mifepristone dispense and will be titrated per LPCH protocol. Amniotomy will performed at the discretion of the provider.

Maternal pulse and blood pressure will be recorded during the ripening process to assess for the incidence of maternal blood pressure or maternal heart rate changes; mean arterial pressures and

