pulse measurements will be recorded every 15 minutes for the first hour of the induction process and then hourly during the first 4 hours of the induction process. If 2 vital sign abnormalities are noted during this period, the OB provider will be notified, and the standard of care work up will be initiated. (See section 2.3.2) Abnormal vital signs include Heart rate > 110 beats per minute or <50 beats per minute, systolic blood pressure (mm Hg) > 160 or < 45 or diastolic blood pressure > 110 or < 85 or MAP <65 mm Hg. Patients will assessed for the presence of known potential side effects from mifepristone or misoprostol by patient interview on postpartum day one. All patients will undergo continuous electronic fetal heart rate monitoring and tocometry until the time of delivery.

Cervical exams will be performed per standard of care by OB providers and recorded. The primary outcome is time to complete cervical dilation. Once the patient achieves complete cervical dilation, time spent in the second stage of labor will be at the discretion of the provider.

Placentas will be sent out to Pathology after delivery if deemed indicated for both groups by the provider. Both groups will have their placentas analyzed if there are clinical indications for the test.

Time and mode of delivery will be recorded into the REDCap database.

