7.2 Management of patient's intolerance to study intervention

Most common adverse reactions (>15%) to mifepristone include nausea, weakness, fever/chills, vomiting, headache, diarrhea, and dizziness.

If the patient experiences side effects, the standard of care medications will be used for the patients:

For nausea and vomiting the patient will be offered Zofran 4 milligrams IV or po every 6 hours as needed, Compazine 10 milligrams IV or po every 6 hours as needed, Reglan 10 milligrams IV or po every 6 hours as needed.

For headache the patient will be offered Tylenol 1 gram po every 8 hours as needed. For diarrhea the patient will be offered Lomotil 5 milligrams every 6 hours as needed. For dizziness and weakness, a comprehensive workup will be established to ensure the etiology is neither infectious or neurological.

As stated in 2.3.2, if the patient experiences 2 vital signs that are outside of normal parameters, the standard of care work up will be initiated.

If the patient experiences a fever in labor, per standard of care, antibiotics are started, and an infectious workup is initiated. If the patient has a fever with abnormal vital signs per CMQCC guidelines (see 2.3.2), assessment for infection is initiated per standard of care.

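### Sections 2.3.2 (adopted by 7.2) and 6.2 both start the standard-of-care work-up at two abnormal vital signs, but they list different signs

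*Combined protocol and SAP*

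**What the plan says.** Section 2.3.2 gives safety measures for mifepristone, and section 2.3.5 extends them to the misoprostol arm. The instruction is "Obtain VITALS (blood pressure, mean arterial blood pressure, heart rate, respiratory rate) throughout labor induction", with temperature taken under the usual unit protocol. A list of limits suggesting circulatory instability or possible sepsis follows. It covers temperature, heart rate, MAP and respiration, the last as "Respiratory rate > 24 breaths per minute or less than < 10 breaths per minute". The trigger is "If the patient experiences 2 vital signs that are outside of normal parameters, the standard of care work up will be initiated". Fever has its own path: on its own it leads to antibiotics and an infectious work-up.

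Section 7.2 has no list of its own and points back: "As stated in 2.3.2, if the patient experiences 2 vital signs that are outside of normal parameters".

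Section 6.2 states the rule again for the conduct of the induction. It begins "Maternal pulse and blood pressure will be recorded during the ripening process", and gives the timetable: "pulse measurements will be recorded every 15 minutes for the first hour of the induction process and then hourly during the first 4 hours". The trigger is "If 2 vital sign abnormalities are noted during this period, the OB provider will be notified", with the same work-up to follow. It then cites section 2.3.2 and introduces, with the word *include*, its own list: heart rate, systolic pressure, diastolic pressure and MAP.

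**The concern.** The protocol's introduction describes the document as a working reference for staff, study nurses among them. A bedside trigger in such a manual should give one answer for one set of readings. Here two sections use the same count and lead to the same action, and one cites the other as if they agreed, yet the lists differ.

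The missing items bear on risks the protocol itself raises. Section 2.3.2 reports serious bacterial infection, including very rare fatal septic shock, after mifepristone, while saying that no causal link is established. Respiration and low temperature are absent from the 6.2 list. Severe gestational hypertension is an exclusion criterion, and upper pressure limits are absent from the readable 2.3.2 list. At stake is whether a participant with a given set of readings is worked up whichever section staff have in front of them.

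**Working it through.** The plan gives no figure to reproduce. The check sets the two lists side by side and applies each to illustrative readings.

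| Item | 2.3.2 (and 7.2 by reference) | 6.2 |
|---|---|---|
| Temperature | below 36 or above 38 °C | not listed |
| Heart rate | above 110 or below 50 | above 110 or below 50 |
| Respiratory rate | above 24 or below 10 | not listed |
| Systolic | not listed | above 160 or below 45 |
| Diastolic | not listed | above 110 or below 85 |
| MAP | below 65 | below 65 |
| Count needed | 2 | 2 |
| Window in trigger sentence | none | *this period* |

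Each list has four signs and two are shared, so 4 + 4 − 2 = 6 signs appear in all.

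Assumptions: MAP = (systolic + 2 × diastolic) / 3, which the protocol does not state; any sign not mentioned is normal; all readings fall in the first 4 hours, so the window plays no part.

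**Case 1.** Pulse 118, respirations 28, 120/90 mm Hg, afebrile. MAP = (120 + 180) / 3 = 100.
- 2.3.2: heart rate (118 > 110) and respiration (28 > 24). Count 2, work-up.
- 6.2 as printed: heart rate only; 120, 90 and MAP 100 are inside its limits. Count 1, no work-up.

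**Case 2.** Pulse 115, 165/100 mm Hg. MAP = (165 + 200) / 3 = 121.7.
- 2.3.2: heart rate only; MAP is not below 65. Count 1, no work-up.
- 6.2: heart rate and systolic (165 > 160); diastolic 100 is inside its limits. Count 2, work-up.

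**Case 3.** Temperature 35.8 °C, respirations 26, pulse 90, 125/88 mm Hg. MAP = (125 + 176) / 3 = 100.3.
- 2.3.2: temperature and respiration. Count 2, work-up.
- 6.2 as printed: count 0.

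Case 2 has only one abnormal pressure value, so it does not depend on whether systolic and diastolic from one reading count separately. It also does not use the lower pressure limits in 6.2. Case 1 does depend on the diastolic chosen: at 120/75 the printed lower diastolic limit in 6.2 would add a second abnormality, and both sections would trigger.

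**Window.** The recording timetables in 2.3.2 and 6.2 are the same: frequent in the first hour, then hourly within the first 4 hours. The trigger sentences differ. In 6.2 the rule is tied to *this period*, which could mean those 4 hours or the ripening process named just before. In 2.3.2 and 7.2 the rule has no window.

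**The case against.** The strongest reply is that the sections are cumulative. Section 6.2 cites 2.3.2 and its list opens with *include*, so it need not be exhaustive; all sections bind the same inpatient, and nothing tells staff to follow one and ignore another. This is a fair reading and it resolves cases 1 and 3, because respiration and temperature then come into 6.2 from 2.3.2. It does not work in reverse. Sections 2.3.2 and 7.2 do not refer to 6.2, so a reader of either finds no upper pressure limit and counts one sign in case 2.

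A second reply is that the 2.3.2 list is aimed at instability and sepsis, that blood pressure is among the vitals taken there, and that its trigger speaks of normal parameters in general. In addition, a figure directly above the list and the sepsis flow chart are not available. This stands as a limit on the finding: the absence of an upper pressure limit in 2.3.2 is established for the readable text only. It does not explain why 6.2 attaches the same count and the same action to a different list.

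Third, fever is already dealt with on its own. That is right, so the temperature difference matters mainly for low temperature.

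Fourth, the timetables match, so a difference in period is not clear. That also stands, and the window is treated here as an ambiguity only.

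**Conclusion.** The point holds as an inconsistency between sign lists. Two of the six signs are common to both, and illustrative readings give opposite answers in both directions within the first 4 hours. Case 2 is the firmer example: it survives the cumulative reading as far as the text of 2.3.2 and 7.2 goes. Case 1 needs the 6.2 list to be taken as printed and the diastolic to lie within its limits. The readings are examples; the documents give no basis for saying how often such a disagreement would occur.

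Several stronger readings are not supported.
- A reader might infer that the 6.2 trigger covers only a small part of labor, by setting 4 hours against the 20-hour average in section 2.2. That takes the narrow meaning of *this period*, uses a time that runs from admission and not from the start of induction, and overlooks that 2.3.2 and 7.2 still apply later.
- A reader might take a severe-range pressure with a normal pulse, such as 170/115 mm Hg, as a clear trigger under 6.2. It counts two only if systolic and diastolic from one reading count separately, which no section states.
- A reader might infer that entry in the safety record depends on which section is followed. Sections 10 and 10.2 define reportable events by their nature and do not refer to this trigger.
- Nor do the documents show that the arms would be handled differently, since section 2.3.5 applies the 2.3.2 measures to the misoprostol arm.

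The matter should be corrected because it is a safety instruction. It does not affect the sample size or the planned comparisons.

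**What to change.** Reconcile sections 2.3.2, 6.2 and 7.2 into one trigger, written out once and cited from the other places. It should give:

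- one list of signs;
- one period, with a stated start and end;
- one statement of whether systolic, diastolic and MAP from the same reading count once or separately.

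The clinical team sets every limit and the period; no view is taken here on which printed values are right.

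The cost is an amendment to wording. Section 2.3.2 already calls for all of these signs to be taken, so no new measurement is needed.

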1.5.1 Protocol Amendments

All protocol changes must be sent to an IRB as protocol amendments.

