2.3.5 Assessment of potential risks

No studies indicate that intrapartum exposure to misoprostol (or other prostaglandin cervical ripening agents) has any long-term adverse health consequences to the fetus in the absence of fetal distress, nor is there a plausible biologic basis for such a concern. Although misoprostol currently is approved by the U.S. Food and Drug Administration (FDA) for the prevention of peptic ulcers, the FDA in 2002 approved a new label on the use of misoprostol during pregnancy for cervical ripening and for the induction of labor. This labeling does not contain claims regarding the efficacy or safety of misoprostol, nor does it stipulate doses or dose intervals.¹

According to the FDA, the major adverse effect of the obstetrical use of misoprostol is hyperstimulation of the uterus which may progress to uterine tetany. There is an increase in uterine rupture (requiring surgical repair, hysterectomy, and/or salpingo-oophorectomy) among patients with a known history of a previous uterine surgery.

There may be an increased risk of uterine tachysystole, meconium passage, meconium staining of amniotic fluid, and Cesarean delivery due to uterine hyperstimulation with the use of higher doses of misoprostol. In this study, the standard dose of 50 mcg and 100 mcg as the second dose if indicated will be used. It is established that oral misoprostol reduces risk for cesarean section rate and has a low incidence of uterine hyperstimulation.⁵ The risk of uterine rupture increases with advancing gestational ages and with prior uterine surgery, including cesarean birth and these patients are excluded from this study.

The following have been reported as adverse events in subjects receiving misoprostol: Gastrointestinal: In subjects receiving misoprostol 400 or 800 mcg daily in clinical trials, the most frequent gastrointestinal adverse events were diarrhea and abdominal pain. The incidence of diarrhea at 800 mcg in controlled trials in patients on NSAIDs ranged from 14-40% and in all studies (over 5,000 patients) averaged 13%. Abdominal pain occurred in 13-20% of patients in NSAID trials and about 7% in all studies, but there was no consistent difference from placebo. However, patients will not receive doses greater than 100 micrograms, minimizing the risk for gastrointestinal side effects.

Due to potential risks of misoprostol, the same safety guidelines as stated in 2.3.2 will remain in this study group.

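### Section 6.2 prints implausible low blood-pressure limits (systolic <45, diastolic <85), probably transposed, so an ordinary 118/76 counts as one of the two abnormal signs that prompt a work-up

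*Combined protocol and SAP*

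**What the plan says.** Section 6.2 (Induction of Labor: Study Groups) has pulse and pressure recorded every 15 minutes in the first hour and hourly up to 4 hours. Abnormal values are heart rate above 110 or below 50, and "systolic blood pressure (mm Hg) > 160 or < 45 or diastolic blood pressure > 110 or < 85 or MAP <65 mm Hg". The action rule is "If 2 vital sign abnormalities are noted during this period, the OB provider will be notified", followed by the usual work-up. The section refers the reader to 2.3.2.

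Section 2.3.2 has a list headed "Vital signs which suggest hemodynamic instability or suspicion for sepsis". Its readable entries are temperature, heart rate (same limits as 6.2), MAP below 65, and "Respiratory rate > 24 breaths per minute or less than < 10 breaths per minute". It gives no systolic or diastolic limit. A figure and a sepsis flow chart in that section are not shown in the text available for this review.

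No other section corrects or explains the values 45 and 85.

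**The concern.** A diastolic floor 40 mm Hg above the systolic floor makes no clinical sense, because diastolic pressure is always the lower of the two. Taken literally, the only normal diastolic range is 85 to 110, so ordinary readings are classed as abnormal. The low systolic limit is so extreme that it does no work.

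These limits feed an action rule. A normotensive participant starts with one of the two required signs already counted and needs only one more. The table of physiological changes in 2.3.2 says pregnancy raises heart rate by 10 to 20 beats per minute, which moves participants toward the 110 limit. The schedule gives about seven readings each (four in the first hour, then three hourly). At stake are unneeded notifications and work-ups, and a written rule that staff would have to ignore in order to act sensibly.

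**Working it through.** **Inputs.** The limits and the two-sign rule come from 6.2, and the comparison list from 2.3.2. The example readings are illustrations, not trial data. Temperature and respiratory rate are taken as normal. MAP = (SBP + 2 × DBP)/3 is the usual approximation and is not stated in the documents.

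**Consistency within the sentence in 6.2**

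- Gap between the low limits: 85 − 45 = 40 mm Hg, in the wrong direction.
- MAP lies between diastolic and systolic, so a diastolic of 85 or more means MAP of at least 85, which is 85 − 65 = 20 above the low-MAP limit. Hence every reading with MAP <65 also has diastolic <85.
- Systolic <45 means MAP <45, so it adds no reading that MAP <65 does not already flag.
- Logical check, not a frequency: among the 18,950 integer pairs with SBP 20–220, DBP 10–140 and SBP > DBP, 550 have SBP <45, and all 550 have MAP <65. No pair has MAP <65 with DBP of 85 or more.
- A reading escapes every pressure flag only if diastolic is 85–110 and systolic is at most 160.

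**Abnormal signs counted, heart rate 112 unless shown** (heart rate 112 is itself one sign)

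| Reading | MAP | 6.2 as printed | Low limits transposed | Readable 2.3.2 list |
|---|---|---|---|---|
| 118/76 | (118 + 152)/3 = 90.0 | 2 | 1 | 1 |
| 110/70 | (110 + 140)/3 = 83.3 | 2 | 1 | 1 |
| 130/86 | (130 + 172)/3 = 100.7 | 1 | 1 | 1 |
| 84/56 | (84 + 112)/3 = 65.3 | 2 | 2 | 1 |
| 110/44 | (110 + 88)/3 = 66.0 | 2 | 2 | 1 |
| 118/76, HR 90 | 90.0 | 1 | 0 | 0 |

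Compared with transposed limits, the printed limits add a trigger only when diastolic is 45–84, systolic is at least 85 and exactly one other sign is abnormal. Every pair flagged on pressure by the transposed limits is also flagged as printed.

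**What a correction does to isolated pressure abnormalities.** Section 6.2 does not say whether systolic, diastolic and MAP count as separate signs. If they do, at heart rate 90:

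| Reading | MAP | As printed | Transposed | Both low limits deleted |
|---|---|---|---|---|
| 88/50 | (88 + 100)/3 = 62.7 | 2 | 1 | 1 |
| 165/80 | (165 + 160)/3 = 108.3 | 2 | 1 | 1 |
| 80/50 | (80 + 100)/3 = 60.0 | 2 | 2 | 1 |
| 70/40 | (70 + 80)/3 = 50.0 | 2 | 3 | 1 |
| 170/115 | (170 + 230)/3 = 133.3 | 2 | 2 | 2 |

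If pressure counts as a single sign, each of these five readings is 1 in all three columns.

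**The case against.** The strongest reply is that the error has little reach. Section 6.2 points to 2.3.2. So does 2.3.5 for the misoprostol arm ("the same safety guidelines as stated in 2.3.2 will remain in this study group"), and so does 7.2 ("As stated in 2.3.2, if the patient experiences 2 vital signs that are outside of normal parameters"). Staff using the readable list there would never flag 118/76. The consequence is only a call to the provider and a standard work-up, by clinicians who know a normal pressure when they see one, over the first 4 hours, in 30 participants at one hospital. All of this stands, and it keeps the point minor. It does not cure the line in 6.2, which is current text attached to an action rule.

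A second reply is that transposition is an inference. That also stands. The documents nowhere give systolic <85 or diastolic <45, and the material not shown in 2.3.2 might hold the intended limits. What is firm is that the printed limits clash with MAP <65 in the same sentence. Exchanging the two numbers removes the clash, but the replacement values need clinical confirmation.

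Two stronger readings are tempting. A reader might infer that 118/76 triggers a work-up by itself; it does not, because a second sign is still required. A reader might also infer that 6.2 and 2.3.2 conflict more widely; with part of 2.3.2 not visible, that cannot be claimed.

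**Conclusion.** The point holds as a minor drafting error in a safety trigger. As printed, ordinary diastolic pressures count as abnormal, and the low systolic limit is redundant. The rule loses specificity but keeps some discrimination. No endpoint, power figure or analysis is affected. The documents give no rates for the second sign, so no number of extra work-ups is claimed.

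It would be too strong to say that hypotension goes unflagged, since MAP <65 remains in the list. It would be too comfortable to say that MAP <65 fully covers it, since that is one sign and two are needed. Under separate counting, low MAP triggers alone as printed only because the faulty diastolic limit always accompanies it.

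The example counts rest on the usual MAP formula. The two redundancy results need only that MAP lies between diastolic and systolic. The 118/76 result is the same whether pressure components are counted separately or together; the isolated-pressure results depend on separate counting.

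**What to change.** Have the clinicians confirm and correct the two low limits in 6.2. If they were transposed, print: systolic >160 or <85, diastolic >110 or <45, or MAP <65 mm Hg. The upper limits stay. This clears 118/76 and 110/70 and still flags 84/56 and 110/44.

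Before signing off, the clinicians should know that, if components are counted separately, 88/50 and 165/80 at heart rate 90 go from 2 signs to 1 and no longer trigger alone. Whether that is acceptable, and how components are to be counted, is for them to decide.

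Deleting both low limits and relying on MAP <65 is not recommended. If it is considered, the amendment should state that under separate counting isolated hypotension such as 80/50 or 70/40 would fall to one sign and no longer prompt notification, and that 84/56 and 110/44 would carry no pressure flag at all.

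The cost is a one-line amendment (section 1.5.1: "All protocol changes must be sent to an IRB as protocol amendments") and a notice to staff. It needs no extra data or participants.
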